4.8. Pharmacokinetic Evaluations

PK analysis will be described separately.

4.9. Safety Analyses

All safety analyses will be conducted on the Safety population.

4.9.1. Adverse Events

Adverse events will be coded using MedDRA Version 24.0 – Mar 2021 and displayed in tables and listings using System Organ Class (SOC) and Preferred Term (PT).

Analyses of adverse events will be performed for those events that are considered treatment emergent adverse events (TEAE), where treatment emergent is defined as any adverse event

Statistical Analysis Plan

Sponsor:	Ocular Therapeutix, Inc.		
Protocol:	OTX-DED-2020-201		
Document Version No.:	V1.0	Document Date:	11NOV2021

with onset on or after the first dose of study medication through the end of the study or any event that was present at baseline but worsened in intensity or was considered drug-related by the investigator through the end of the study.

The safety will be assessed by incidence of TEAEs, therefore, in any tabulation, a subject contributes only once to the count for a given adverse event (SOC or preferred term). An overall summary of TEAEs will be presented including the number of events and the number of the subjects with events along with percentages by treatment group and overall. The overall summary will include subjects with AE leading to death, subjects with TEAEs leading to insert removal and subjects with TEAEs leading to subject withdrawal. In summary tables, SOC will be presented alphabetically and events within SOC will be presented by decreasing frequency count based on the total column.

The frequency and percentage of subjects with any TEAE, any serious TEAE, any TEAEs by relationship to treatment (unrelated, related), any serious TEAEs by relationship to treatment (unrelated, related), any TEAE by severity (mild, moderate, or severe) will be summarized separately for ocular and non-ocular events by treatment group and overall. Separate summaries for ocular TEAEs and non-ocular TEAEs by preferred terms in decreasing frequency based on all subjects will be tabulated.

All adverse events will be listed in subject data listings.

By-subject listings also will be provided for the following: subject deaths; serious adverse events; and adverse events leading to withdrawal.

4.9.2. Non-AE Safety Analyses

The following safety assessments will be summarized using descriptive statistics for Safety population by treatment group and overall. Assessments will be presented for study eye and non-study eye separately.

1. Best Corrected Visual Acuity (BCVA)

LogMAR Visual Acuity (VA) score for each visit, its CFB, and loss 3 Lines or more in BCVA LogMAR Score from Baseline at each post-baseline visit will be calculated and summarized using descriptive statistics.

2. Slit-Lamp biomicroscopy

The evaluation of normal, mild, moderate, severe, and very severe for each eye in Eyelid Vascularity (vascular engorgement) and Meibomian Glands (upper and lower lid orifice plugging) , as well as normal, abnormal non-clinically significant, and abnormal clinically significant for each eye in Punctal Appearance, Lid Apposition, Lashes, Conjunctiva,

Sponsor:	Ocular Therapeutix, Inc.		
Protocol:	OTX-DED-2020-201		
Document Version No.:	V1.0	Document Date:	11NOV2021

Sclera, Cornea, Anterior Chamber, Iris, Pupil, and Lens will be tabulated for each visit by using the frequency and percentage.

3. Intraocular Pressure (IOP) measurement (mmHg)

Absolute values and CFB of IOP at each post-baseline visit, absolute IOP measurement \geq 30 mmHg at each visit, and CFB in IOP > 5 mmHg as well as >10 mmHg at each post-baseline visit will be summarized using descriptive statistics.

4. Fundus Examination

The evaluation of normal, abnormal non-clinically significant, and abnormal clinically significant for each eye in vitreous, retina, macula, choroid, and optic nerve exam will be tabulated for visit 1 and visit 7 by using the frequency and percentage. The absolute cup-to-disc ratio at baseline and Visit 7 (Day 57) and its CFB at Visit 7 (Day 57) will be presented using descriptive statistics.

5. Artificial tears use during the study

The use of artificial tears, based on the Daily Subject Diary, since last visit will be tabulated for each post-baseline visit by using frequency and percentage. Number of times AT used since last visit will be reported among all subjects who have any daily subject dairy data since the last visit using descriptive statistics.

4.9.3. **Laboratory Data**

Safety laboratory tests will not be collected. Urine pregnancy test results will be captured at Visit 2 (Day 1) and Visit 7 (Day 57). Urine pregnancy test results will be provided in data listing.

4.9.4. **Vital Signs and Physical Examinations**

Vital signs and physical examinations data will not be collected.

4.9.5. **Concomitant Medications**

Concomitant medications will be coded using the WHO Drug dictionary, DD B3 WHO Drug DDE – Sep 2020. Results will be tabulated by Anatomic Therapeutic Class (ATC) and preferred term.

Concomitant medications will be defined as those medications that were initiated after study drug administration or those that were ongoing at the time of study drug administration. If the start date or end date of a medication is partially missing, the date will be compared as far as possible with the date of the start of administration of study drug. The medication will be

Statistical Analysis Plan

Sponsor:	Ocular Therapeutix, Inc.		
Protocol:	OTX-DED-2020-201		
Document Version No.:	V1.0	Document Date:	11NOV2021

assumed to be prior medication if it cannot be definitively shown that the medication did not start or continue during the treatment period.

Non-ocular prior and concomitant medications will be summarized by higher ATC level 3 (therapeutic subgroup) and preferred term by treatment group and overall, in the Safety population. ATC Level 3 terms will be sorted alphabetically. Preferred terms will be sorted by descending frequency overall within ATC Level 3 term. Subjects receiving a particular medication or medication of ATC Level 3 will be counted once at the preferred term level and once at ATC Level 3.

Ocular prior and concomitant medications will be summarized at the eye level, separately for study and non-study eyes, and at the subject level (both eyes) by ATC Level 3 and preferred term by treatment group and overall, in the Safety population.

All prior and concomitant medications information will be presented in the data listing.

Sponsor:	Ocular Therapeutix, Inc.		
Protocol:	OTX-DED-2020-201		
Document Version No.:	V1.0	Document Date:	11NOV2021

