	
Subjects will undergo Screening within 14 \pm2 days prior to Insertion/Day 1 (Visit 2). At Visit 2 (Insertion/Day 1) subjects confirmed to be eligible will be randomly assigned to one of three treatment groups (OTX-DED 0.2 mg, OTX-DED 0.3 mg, or HV) in a 1:1:1 ratio. OTX-DED or HV insert, as applicable, will be placed bilaterally, into either the superior or inferior canalculus (per investigator's preference). The treatment follow-up visits will occur at Week 1/Day 8 (Visit 3), Week 2/Day 15 (Visit 4), Week 3/Day 22 (Visit 5) and Week 4/day 29 (Visit 6). All subjects will be followed until Week 8/Day 57 (Visit 7) to evaluate whether or not the insert is visualized.

Inclusion Criteria	
Subjects will be eligible for study participation if they:
 
 1. Provide written informed consent prior to performing any study procedures and are willing to comply with study requirements and the study visit schedule. 2. Are 18 years of age or older. 3. Have a self-reported history or clinically confirmed diagnosis of DED by an eye care professional in both eyes for \geq6 months. 4. Have ongoing DED, at screening visit as defined by the following criteria: 
 a. VAS Eye Dryness severity score \geq 40. And in the same qualifying eye or both eyes: 
 b. Investigator assessment of bulbar conjunctival hyperemia grade \geq 2 (CCLRU; 0 – 4 scale). c. Unanesthetized Schirmer of > 0 and \leq 10 mm. 5. Have corrected visual acuity better than or equal to logarithm of the minimum angle of resolution (logMAR), +0.7 as assessed with Early Treatment of Diabetic Retinopathy Study (ETDRS) charts in both eyes. 6. Are women of childbearing potential (WOCBP) who are non-pregnant, non-lactating, and sexually inactive (abstinent) for 14 days prior to screening and are willing to remain so through the last study visit. Alternatively, WOCBP who are not abstinent must have been using one of the following acceptable methods of birth control for the times specified: 
 a. Intra-uterine device (IUD) in place for at least 3 months prior to screening and the desire to continue this method through the last study visit. b. Barrier method (condom or diaphragm) with spermicide for at least 14 days prior to screening and the desire to continue this method through the last study visit. c. Stable hormonal contraceptive for at least 3 months prior to

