4.2.9. Missing, Unused, and Spurious Data

If the start date of an AE is partially or completely missing, the date will be compared as far as possible with the date of the start of administration of study drug. The AE will be assumed to be treatment-emergent if it cannot be definitively shown that the AE did not occur or worsen during the treatment-emergent period (worst case approach). The imputed dates will only be used to classify events as treatment emergent and will only be used in the table analyses. Listings will display the available date data.

The following general rules will be used:

- If the start day is missing but the start month and year are complete, an AE will only be excluded as being treatment-emergent if the start month/year is before the month/year

Sponsor:	Ocular Therapeutix, Inc.		
Protocol:	OTX-DED-2020-201		
Document Version No.:	V1.0	Document Date:	11NOV2021

of study drug administration or if the date of resolution is before study drug administration.

- If the start day and month are missing but the start year is complete, an AE will only be excluded as being treatment-emergent if start year is before the year of study drug administration or if the date of resolution is before study drug administration.
- If the start date is completely missing, an AE will be considered treatment-emergent unless the date of resolution is before study drug administration.

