4.6. Treatment Exposure

Details of study drug administration, including duration of treatment will be tabulated and presented for the Safety population. The duration of exposure will be calculated in days as latest date investigator confirms insert is not present in either eye minus date of the earliest insertion in either eye plus 1 and summarized using descriptive statistics by treatment group and

Sponsor:	Ocular Therapeutix, Inc.		
Protocol:	OTX-DED-2020-201		
Document Version No.:	V1.0	Document Date:	11NOV2021

overall. Treatment exposure for subjects who discontinue the study prior to the insert no longer being present in both eyes, will be calculated in days as date of last insert visualization in either eye minus date of the earliest insertion in either eye plus 1. In addition, treatment exposure for subjects who discontinue the study prior to the insert no longer being present in both eyes will be set to the longest observed insert exposure as an additional analysis.

All dosing information will be presented in a data listing.

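### SAP 4.9.5 resolves an undecidable medication date to 'prior', the reverse of the SAP's own adverse-event rule

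*SAP*

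**What the plan says.** SAP 4.9.5 (Concomitant Medications) defines concomitant medications as "those medications that were initiated after study drug administration or those that were ongoing at the time of study drug administration". It gives no separate definition of prior medication; prior is what remains when the definition is not met.

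The section then turns to incomplete dates. The rule is triggered by "If the start date or end date of a medication is partially missing". The date is to be compared with the start of study drug as far as the available parts allow, and the medication is then "assumed to be prior medication if it cannot be definitively shown that the medication did not start or continue during the treatment period".

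SAP 4.2.9 (Missing, Unused, and Spurious Data) has the matching rule for adverse events with incomplete start dates, which reads in part: "The AE will be assumed to be treatment-emergent if it cannot be definitively shown that the AE did not occur or worsen during". The interval meant is the one on treatment, and the SAP labels this a worst-case approach. Its bullets apply it: with only the start day missing, an event is taken out of the treatment-emergent set only if its start month precedes the month of dosing or it resolved before dosing.

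SAP section 5 (Changes to Planned Analyses) does not mention medication dates. No reason for treating medications differently is given elsewhere in the SAP or the protocol.

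**The concern.** The two rules share a construction: if it cannot be shown that something did not happen during treatment, assume a category. For adverse events the assumed category is the on-treatment one. For medications it is the pre-treatment one. The purpose of the prior/concomitant label is to tell the reader whether use may have overlapped treatment. A default that assigns 'prior' exactly when overlap cannot be ruled out works against that purpose.

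The likeliest explanation is a one-word drafting slip. It still matters in a prespecified plan, because the programmer must either code a default that points the wrong way or depart from the text without a record. What is at stake is the correct labelling of medications with incomplete dates in the safety-population summaries and listings.

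**Working it through.** The plan states no figure on this point, so there is none to reproduce. The check applies the rules to every possible date pattern.

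**Inputs**

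- Concomitant: started after, or ongoing at, study drug administration (SAP 4.9.5).
- Default for incomplete medication dates: prior when use during treatment cannot be excluded (SAP 4.9.5).
- Comparator default: on-treatment when occurrence during treatment cannot be excluded (SAP 4.2.9).
- Assumptions, not from the documents: dates known to month and year only; insertion on day 15 of month M; stop not before start.

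**Test for each pattern.** Overlap is certain if the earliest possible stop is on or after insertion, or use is ongoing. It is excluded if the latest possible stop is before insertion. Otherwise it is unresolved.

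| Start | Stop | Overlap | Definition first, then default | Sentence alone | With 'concomitant' as default |
|---|---|---|---|---|---|
| before M | before M | excluded | prior | condition not met, no label | prior |
| before M | in M | unresolved | prior | prior | concomitant |
| before M | after M | certain | concomitant | prior | concomitant |
| before M | ongoing | certain | concomitant | prior | concomitant |
| in M | in M | unresolved | prior | prior | concomitant |
| in M | after M | certain | concomitant | prior | concomitant |
| in M | ongoing | certain | concomitant | prior | concomitant |
| after M | after M | certain | concomitant | prior | concomitant |
| after M | ongoing | certain | concomitant | prior | concomitant |

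**Counts**

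- Patterns: 1 excluded + 2 unresolved + 6 certain = 9.
- Definition first, then the default as written: prior in 1 + 2 = 3 of 9, of which 2 arise from the reversed default.
- Sentence applied on its own: prior in 2 + 6 = 8 of 9. In the ninth its condition is not met, so it assigns nothing.
- Default changed to 'concomitant': prior in 1 of 9, concomitant in 2 + 6 = 8 of 9.

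**One unresolved case.** Suppose insertion is on 15 March, and a medication was started in January and stopped on an unknown day in March. Of the 31 possible stop days, 14 (1 to 14 March) fall before insertion and 17 (15 to 31 March) fall on or after it. The dates cannot decide. SAP 4.9.5 calls the medication prior. An adverse event with its start day unknown in the same March, and no earlier resolution, is treatment-emergent under SAP 4.2.9. The same kind of doubt is resolved in opposite directions.

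**The case against.** The strongest defence is the order of the text. SAP 4.9.5 defines concomitant first, then calls for comparing the available date parts with the start of study drug, and only then gives the assumption. Read in that order, every date that settles the question is classified by the definition, and the default governs only the unresolved ones. For those the definition has nothing to say, so there is no internal contradiction, only a different default from the adverse-event rule. This stands as a limit on reach: known use during treatment stays concomitant. It does not rescue the default, which still sends both unresolved patterns to 'prior' without a stated reason.

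A reader might infer more: that no medication with a partial date can ever be concomitant, so that all nine patterns end as prior. The documents do not support that. Reaching nine requires the definition to make the excluded pattern prior while ignoring the same definition for the six certain patterns. Applied consistently, the text gives 3 of 9, or 8 of 9 from the sentence alone.

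A reader might also infer that use during treatment would be hidden, or that the per-protocol set would be affected. Neither follows. SAP 4.9.5 names prior and concomitant medications together in both the ocular and non-ocular summaries, specifies no separate tables, and lists all of them. If they are tabulated together, no count changes. Under SAP 3.1 and 3.2, per-protocol exclusions rest on a review of deviations before unmasking and on a count of artificial-tear drops, not on this label. Artificial-tear use is tabulated from the diary (SAP 4.9.2).

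**Conclusion.** The default in the partial-date sentence of SAP 4.9.5 is reversed relative to SAP 4.2.9, and this holds on either reading. On the reading more favourable to the plan, it puts the 2 unresolved patterns of 9 under 'prior' where the adverse-event approach would make them concomitant. On the literal reading it also conflicts with the section's own definition in the 6 certain patterns.

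The pattern counts rest on month-only dates and a mid-month insertion. They do not cover year-only dates or a mix of one complete and one partial date, and they say nothing about how often each pattern will occur. The number of medications with incomplete dates is not given.

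The consequence is minor. Only the prior/concomitant label in the medication summaries and listings can change. No adverse-event rate, efficacy result or analysis-population membership depends on it.

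**What to change.** In the partial-date sentence of SAP 4.9.5, replace 'prior' with 'concomitant'. The default then agrees with the adverse-event rule in SAP 4.2.9, and with the definition in SAP 4.9.5 wherever the dates allow the definition to decide.

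The cost is one word in the SAP, with the classification programmed to match. Data collection does not change.

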5. CHANGES TO PLANNED ANALYSES

The primary, sensitivity, and secondary efficacy endpoints will be analyzed using both mITT and PP populations.

Protocol pre-specified primary analysis is multiple imputation using MCMC with Dunnett's adjustment. Upon further technical research, multiple imputation using MCMC with Dunnett's adjustment can't be correctly implemented. Due to the current limitation of multiple imputation with multiplicity correction, the primary analysis will be conducted using observed data with Dunnett's adjustment.

For sensitivity analyses, MCMC MI, LOCF, and FCS MI will be used. For analyses using MCMC MI and FCS MI, for treatment comparisons, least square means will not be adjusted for multiple comparison and for the unadjusted treatment group comparisons, only t-test will be used.

For severity and frequency eye dryness (VAS), investigator assessment of bulbar conjunctival hyperemia, and tCFS and its sub-regions, the main analysis will be based on observed data and sensitivity analyses will be done using MCMC MI, LOCF, and FCS MI.

For the presence of insert, the groups will be compared using observed data by Fisher's exact test. Clopper-Pearson method will be used to calculate 95% confidence interval of the proportion of subject with presence of insert; to calculate 95% confidence interval of the proportion difference, the Chan and Zhang (1999) method will be used.

Sponsor:	Ocular Therapeutix, Inc.		
Protocol:	OTX-DED-2020-201		
Document Version No.:	V1.0	Document Date:	11NOV2021

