4.2.6. Multiple Comparisons/Multiplicity

To control the type I error for the hypothesis testing of the primary endpoint, least square means will be used to make treatment comparisons using Dunnett's adjustment for multiple comparisons to a control.

As this is a Phase 2 study, no adjustments to alpha will be made for testing of multiple endpoints.

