4.2.9.1. Imputation Method for Primary Efficacy Endpoints

To impute missing, Markov Chain Monte Carlo (MCMC) multiple imputation (MI), Fully Conditional Specification multiple imputation (FCS MI) and LOCF methods will be used.

For MI, we will have below phases:

1. Imputation Phase: in this phase, the missing data will be imputed using SAS PROC MI and a complete data set will be created. This process of imputation will be repeated 25 times. Therefore, 25 compete datasets will be created. In this phase, treatment group, baseline value, and post-baseline visits will be included in multiple imputation model.
2. Analysis Phase: each of the 25 complete data sets will be analyzed independently using desired statistical method (e.g. ANCOVA for primary efficacy analysis).
3. Pooling Phase: in this phase the estimates obtained from each analyzed complete dataset from phase 2, will be combined using PROC MIANALYZE.

The primary analyses of efficacy data will use MCMC MI methodology to impute missing data. The expectation and maximization (EM) algorithm will be used to estimate the mean vector and the covariance assuming a missing at random (MAR) distribution. The MAR distribution assumes the probability that a value is missing does not depend on the true values of the missing items. The imputation phase will create 25 copies of the dataset which will contain different estimates of the missing values. The 25 complete datasets will then be analyzed to produce several sets of parameter estimates and standard errors, which will then be pooled to create a single set of results.

Last observation carried forward (LOCF) method and Fully Conditional Specification multiple imputation (FCS MI) with 200 burn-in iterations and 25 times of imputation under the assumption of missingness at random will be used for sensitivity analyses (Section 4.7.2).

Sponsor:	Ocular Therapeutix, Inc.		
Protocol:	OTX-DED-2020-201		
Document Version No.:	V1.0	Document Date:	11NOV2021

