4.7.1. Primary Analyses

For the primary efficacy endpoint analyses of change from baseline in photographic assessment of bulbar conjunctival hyperemia (evaluated by central reading center) worst zone in the study eye at Visit4 (Day 15) (as defined in section 2.6.1.1), the following modeling and analyses will be performed on mITT population, observed data:

An analysis of covariance (ANCOVA) model will be run to estimate least square (LS) means treatment. This model will include the baseline value as a covariate for adjustment and treatment group as the sole factor. Least square means will be used to make treatment comparisons using Dunnett's adjustment for multiple comparisons to a control. Statistical significance of treatment differences will be determined using a two-sided significance level of $\alpha = 0.05$.

In the ANCOVA model, LS means treatment group comparison of OTX-DED 0.2 mg to HV, OTX-DED 0.3 mg to HV, and Overall OTX-DED (combined OTX-DED 0.2 mg and OTX-DED 0.3 mg using sample size weights of OTX-DED 0.2 mg and OTX-DED 0.3 mg groups as coefficients for the parameters) to HV will be reported. Unadjusted treatment group analyses using two-sample t-test and Wilcoxon rank sum test will be run on these treatment group combinations.

Each bulbar conjunctival hyperemia zone (Nasal, Temporal, and Frontal) and the Total of the three zones in study eye will be analyzed in a manner similar to the primary efficacy variable as described above.

The same analyses will be done for the non-study eye. For non-study eye, the worst zone similar to worst zone in study eye (details in section 2.6.1.1) will be independently determined using photographic assessment bulbar conjunctival hyperemia in non-study eye at baseline.

Sponsor:	Ocular Therapeutix, Inc.		
Protocol:	OTX-DED-2020-201		
Document Version No.:	V1.0	Document Date:	11NOV2021

The primary efficacy endpoints will also be analyzed on PP population.

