4.7.2. Sensitivity Analyses

To determine robustness of results, the sensitivity analyses will be performed for the primary efficacy endpoint, bulbar conjunctival hyperemia at Visit4 (Day 15), on the mITT and PP populations by using:

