1. MCMC MI
2. last observation carried forward (LOCF)
3. FCS MI.

As sensitivity analyses, LOCF will be analyzed in a manner similar to the primary efficacy variable (details in section 4.7.1). MCMC MI and FCS MI will be analyzed in a manner similar to the primary efficacy variable (details in section 4.7.1), however, for treatment comparisons, least square means will not be adjusted for multiple comparison and for the unadjusted treatment group comparisons, only t-test will be used.

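### The SAP leaves both multiple-imputation sensitivity analyses without multiplicity correction because of a limitation specific to Dunnett, and for photographs those analyses nearly duplicate the observed-data primary

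*SAP*

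**What the plan says.** - **Primary analysis.** SAP 4.7.1 sets the ANCOVA of Day 15 change, baseline-worst photographic zone, study eye: "the following modeling and analyses will be performed on mITT population, observed data". The model has treatment and baseline, with Dunnett for each dose against hydrogel vehicle (HV). SAP 4.2.6 gives the purpose: "To control the type I error for the hypothesis testing of the primary endpoint".
- **Reason for the change from the protocol.** SAP 5 says that "multiple imputation using MCMC with Dunnett's adjustment can't be correctly implemented" and concludes: "Due to the current limitation of multiple imputation with multiplicity correction, the primary analysis will be conducted using observed data".
- **Sensitivity analyses.** SAP 4.7.2 lists MCMC MI, LOCF and FCS MI: "To determine robustness of results, the sensitivity analyses will be performed for the primary efficacy endpoint". For LOCF, "LOCF will be analyzed in a manner similar to the primary efficacy variable", so it keeps Dunnett. For both MI analyses, "least square means will not be adjusted for multiple comparison".
- **Leftover text.** SAP 4.2.9.1 still says: "The primary analyses of efficacy data will use MCMC MI methodology to impute missing data".
- **Imputation models.** For photographs, the MCMC code (7.1.1) and the FCS code (7.1.2) use treatment, baseline and Day 15, zone by zone, bounded at 0 to 4 and rounded to integers. Protocol Appendix 6 takes photographs at baseline and Day 15 only.
- **Pooling.** SAP 7.1.3 fits the ANCOVA to each imputed dataset and pools each labelled contrast separately.

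**The concern.** The premise in SAP 5 is about Dunnett within MI. The conclusion is wider: the MI analyses get no correction of any kind. Analyses meant to show that a Dunnett-adjusted result is robust then sit on two scales, with LOCF adjusted and both MI analyses not. A dose could reach nominal significance in an MI table when the primary does not, and a reader could credit the handling of missing data for what is only the dropped adjustment.

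The photographic MI has a second weakness. If the imputation model holds the same variables as the analysis model, agreement between the two is close to guaranteed and says little about bias from missing photographs.

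**Working it through.** **Inputs from the documents.** 150 subjects, 1:1:1, so 50 per arm; two-sided alpha 0.05; ANCOVA with an intercept, two treatment terms and baseline, so df = 150 − 4 = 146. The documents give no effect size, SD, dropout rate or power, so there is no plan figure to reproduce.

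**1. Familywise error of the two dose contrasts, no missing data.** The contrasts share the HV arm. Correlation = (σ²/50) / (σ²/50 + σ²/50) = 0.5. Familywise error = 1 − P(|T1| ≤ c and |T2| ≤ c) for a bivariate t with 146 df.

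| Rule | Critical t | Per-contrast p | Familywise error |
|---|---|---|---|
| Unadjusted | 1.976 | 0.05 | 9.1% |
| Dunnett | 2.234 | 0.027 | 5.0% |
| Bonferroni | 2.265 | 0.05/2 = 0.025 | 4.6% |

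Holm tests the smaller p at 0.025 and the larger at 0.05, and has the same familywise bound. Both rules need only the two p-values that SAP 7.1.3 already pools. The overall-dose contrast lies outside the Dunnett family in 7.1.5 and can stay outside here.

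**2. Why photographic MI tracks the primary.** The analysis regresses (Day 15 − baseline) on treatment and baseline. Because baseline is a covariate, the treatment coefficient equals that from regressing Day 15 itself on the same terms. MI fits that regression to the observed cases and draws missing values around the fitted line. Points placed on a least-squares line leave the line unchanged, and the random draws average out over 25 imputations. What remains comes from rounding, the 0 to 4 bounds, and imputing each zone across all study eyes before the worst zone is picked.

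**3. Size of that remainder, by simulation.** Assumptions: 50 per arm; three zones, correlation 0.6; integer grades 0 to 4; latent SD 0.75; baseline mean 2.3; HV change −0.3; baseline to Day 15 latent correlation 0.6; 25 imputations; 5/10/20% missing at random.
- Correlation of MI with observed-data estimates: 0.998/0.996/0.988. SD of the difference: 0.009/0.014/0.024 grade.
- A second model, with missingness depending on baseline and arm: correlation 0.997/0.993/0.978, SE ratio 1.013 to 1.025.

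**4. Effect of the missing adjustment, first model, 5/10/20% missing.**
- Null, at least one dose significant: primary 5.0/5.1/5.1%; MI unadjusted 8.4/7.5/6.2%; MI with Holm 3.9/3.6/3.0%. The 9.1% in step 1 is therefore a no-missing-data figure.
- Effect −0.28 grade, where the primary succeeds in 55/54/48% of trials: MI unadjusted is significant and the primary is not in 9.4/9.3/8.4%. In 92/91/84% of those trials the unadjusted observed-data contrast is significant too, so the adjustment explains most of the gap.
- Disagreement in either direction: 9.4/9.4/9.0% as planned, 2.8/4.8/7.5% with Holm.

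**5. Gain from investigator grades as auxiliary variables.** Effect −0.50, Visit 2 and Day 8 grades added. For Day 8 grade to Day 15 photograph correlations of 0.34/0.55/0.71, root mean squared error against full data falls by 0/8/22% at 10% random missing, and by 1/10/27% when dropout depends on the Day 8 grade. In that second case the bias is 0.003/0.008/0.013 grade as coded and 0.001/0.002/0.003 with the added grades. A simpler single-zone model gave reductions of 3–5%, 12–15% and 19–31% at latent correlations 0.35, 0.6 and 0.8.

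**The case against.** The best defence is that nothing is hidden and little hangs on it. SAP 4.7.2 and 5 both state that the MI comparisons are unadjusted. SAP 4.2.6 confines type I error control to the primary endpoint test, and robustness is properly judged on estimates and intervals, which Holm does not alter. SAP 4.7.1 already reports the LS-means contrasts and plans unadjusted t-tests on observed data; 4.7.2 plans the matching t-tests on MI data. A like-for-like comparison therefore exists, and setting the unadjusted contrasts side by side is mostly layout. All of this stands. It does not rescue the stated rationale, which treats a Dunnett limitation as a bar to any correction.

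Holm is also imperfect. It is slightly stricter than Dunnett, and at 20% missing it lowers disagreement only from 9.0% to 7.5%. The −0.28 effect was chosen where adjusted and unadjusted results diverge readily. Both limits are accepted.

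On the imputation models, auxiliary variables still assume MAR, and the simulated bias is at most 0.013 grade. Whether zone-level investigator grades exist is also unclear: SAP 2.6.1.2, 4.7.3 and 7.1.1 treat them as collected, while Protocol Appendix 5 describes one overall rating.

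Three stronger readings are tempting, and the documents do not support them:
- A reader might infer from SAP 4.2.9.1 that the primary is undetermined. SAP 5 declares the change, as Protocol 10.9 requires, and 4.7.1 and 4.7.2 agree with it.
- A reader might infer that the trial's primary error rate is inflated. The primary keeps Dunnett.
- A reader might infer that missing data go unexamined, or that MI and the primary are identical. LOCF is a different check: with one post-baseline photograph it presumably carries baseline forward, giving zero change. Zone-wise imputation and rounding leave small differences between MI and the primary.

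**Conclusion.** The point holds, at minor to moderate weight. The error figures in step 1 rest only on the planned sample size and model. All other figures depend on assumed missing rates, SD and correlations, because the documents give none.

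- The reason in SAP 5 supports dropping Dunnett from the MI analyses. It does not support leaving them uncorrected.
- For photographs, the two MI analyses add little as a missing-data check. LOCF is the only planned analysis that departs materially from the primary.
- The sentence in SAP 4.2.9.1 is an editorial leftover.

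The study is stated to be unpowered and descriptive, so the consequence lies in how the sensitivity tables are read. The validity of the primary result is not affected.

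**What to change.** 1. In the MCMC MI and FCS MI analyses, report Holm- or Bonferroni-adjusted p-values for the two dose-versus-HV contrasts beside the unadjusted results, and note that they are slightly conservative relative to Dunnett. Reword SAP 5 as a limitation of Dunnett within MI. Cost, at 10% missing: the chance that at least one dose is significant in MI falls from 97.7% to 95.5% at an effect of −0.50, and from 63.3% to 50.3% at −0.28 (primary 54.1%). At −0.28, a significant primary goes unmatched by MI in 4.3% of trials, against 0.1% unadjusted. Keeping the unadjusted column in view limits misreading.
2. Add the investigator hyperemia grades (Visit 2, Day 8, and Day 15 where present) as auxiliary variables in the photographic MCMC and FCS models: by zone if zone grades exist, otherwise the overall grade. Reconcile Protocol Appendix 5 with SAP 2.6.1.2, 4.7.3 and 7.1.1 on which was collected. The gain depends on an unknown correlation and is small if that is weak; MAR is still assumed.
3. Amend SAP 4.2.9.1 so that observed data with Dunnett is the single stated primary and MCMC MI is a sensitivity analysis.
4. Optionally, state in one line what LOCF does when the only post-baseline photograph is missing.

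All of this is SAP wording and a few lines of SAS, with no new data collection.
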